### **6.3 Research procedures**

Dedicated uveitis clinics are run in each centre, which will consider all new referrals. Medical and uveitis history will be recorded, screening investigations will be ordered and eligibility will be assessed.

Potentially eligible patients will be consented (to screening and the full study on one consent form) prior to full screening assessments (as per Table 1. Schedule of events during the trial) being done. Patients who are eligible to take part after all required screening assessments are done will be enrolled in the TRI after confirming they are still willing to take part.

Data will be collected on the numbers screened, eligible pre- and post-consent and starting the TRI, including reasons for declining participation. Data will be captured in a purpose-designed secure database, with 'real time' validation, which will be developed by the BTC to support the trial. Resource use data will be collected using bespoke questionnaires and trial case report forms (CRFs).

Participants starting the TRI will be seen at 4 weeks (at hospital), 8 weeks (telephone call review) and 16 weeks (at hospital). This visit frequency approximates usual care, when a patient starts treatment with adalimumab. Study assessments will be completed as per the Schedule of events during the trial (table 1).

At the 16 week visit, if a participant is classified as a responder (see 6.3.1) and agrees to continue in the randomised trial, he/she will be randomised (see 5.7, 5.8.1 and 6.1).

Participants who meet the responder criteria will be randomised into the RCT and will have follow-up visits will be scheduled at 12-weekly intervals up to 48 weeks after randomisation and 16-weekly intervals thereafter, consistent with usual care for patients with ANIU.

If treatment failure is suspected in between 12-weekly follow up visits, an unscheduled treatment failure assessment visit should be conducted to include all follow-up assessments as per the schedule of events. If at an unscheduled visit, TF is NOT confirmed to have occurred the participants will still need to attend the next scheduled visit and all assessments conducted as per protocol.

Participants who consent to donate optional blood serum samples will have these taken at baseline, TRI 16 week visit, (both responders and non-responders) and, if randomised, 48 week visit and 96 week visits in the RCT, and at any post randomisation visit where a participant experiences TF (whether this is observed in the RCT or OLE).

Participant who consent to optional whole blood DNA samples will have these taken at baseline.

Optional serum and DNA will be prepared from the blood samples and stored. These samples, and retinal images taken as part of the study, will be collected and stored as a resource for future studies of markers for (a) responsiveness to adalimumab and (b) TF.

At their last visit before expiry of the placebo, participants who give consent will transition to the OLE (see 5.1 and 5.3). Participants in the OLE will continue with the same visit and treatment schedule as they had in the RCT until they either experience TF (when they will exit the trial) or they reach the end of the OLE period (when they will exit the trial at the last visit before 31st March 2026).

### 6.3.1 Responder criteria

A responder will be defined as meeting ALL of the following criteria at the 16 week TRI visit:

- i. No activity on colour fundus or autofluorescence imaging indicative of inflammatory chorioretinal lesions;
- ii. CMT  $\leq$  320 $\mu$ m on any OCT machine and no evidence from OCT of cystoid macular oedema (CMO)\* [11];
- iii. No evidence of active retinal vasculitis [11];
- iv.  $\leq$  0.5 vitreous haze Binocular Indirect Ophthalmoscopy (BIO) score;
- v. Prescription of  $\leq$  5.0mg/day oral prednisolone to achieve/maintain uveitis remission [11] (participant is a responder if prescribed  $>$ 5.0mg/day oral prednisolone for a co-morbidity (e.g. rheumatic disease) where ALL of i-iv are met).

\* An eye can be classified as a responder if CMT  $>$  320 $\mu$ m providing that there is full clinical resolution, i.e. complete resolution of macular thickening, cysts and intra/subretinal fluid.

### 6.3.2 Investigations during follow-up

Investigations relating to eligibility, data about safety of medications, refraction and imaging will be carried out during the TRI. The following investigations will be carried out at all visits after randomisation (see Table 1):

- a) Ophthalmic examination, including slit lamp examination with dilated funduscopy and tonometry;
- b) Vital signs / weight (every other follow-up visit);
- c) Changes in medications, AEs, adherence to medications
- d) BCVA (ETDRS letter chart) determined by an optometrist masked to treatment allocation;
- e) Retinal imaging, comprising OCT, macular and retinal nerve fibre layer;
- f) Colour fundus imaging in all participants, and autofluorescence and fundus fluorescein angiogram in those where it was required to determine if disease was active or not at baseline.\*
- g) In addition, the following patient-reported outcome measures will be collected: EQ-5D 5L; VCM1; Work Productivity and Activity Impairment Questionnaire: Specific Health Problem Questionnaire (WPAI-SHP); symptoms of side effects.

\*If AF/FFA are required to determine that disease is active or not at baseline, these tests will need to be repeated when establishing responder status or TF.

## 6.4 Duration of treatment period

As described in section 5.1, we have chosen to try to keep participants in the trial until the trial will be close to reporting [53]. Treating with adalimumab for longer than 48 weeks is consistent with how adalimumab is used in practice in patients who are maintained on it successfully, so will contribute valuable longer term evidence about the intervention. This approach is likely to foster better commitment among participants and is supported by the PPI panel.

## 6.5 Definition of end of trial

The RCT will end for a participant after they have completed follow up (including repeat TRIs) for a minimum of 12 weeks up to a maximum of 170 weeks (approx. between 3 and 40 months) post-randomisation, or earlier if they withdraw from the study completely. The OLE will extend

follow-up for another 76 weeks (approx. 18 months). The maximum period any participant could be in the trial is 246 weeks (approx. 58 months).

The end of the RCT will be after all trial participants have completed placebo-controlled follow up in the RCT, all data queries have been resolved and the RCT part of the database has been locked. The end of the OLE will be after all trial participants have completed the last follow up before ending the study, all data queries have been resolved and the OLE part of the database has been locked. Data from the OLE will be used to update estimates of treatment effectiveness.

Data collection

Data collection will include the elements described in Table 1.

**Table 1 Schedule of events during the RCT and OLE**

No.	Data item to be collected	Screen/ baseline	Treatment run-in				RCT / OLE					
			1 st injection (wk 0)	4 w	8 w (phone call)	16 w / Rx	12 w	24 w	36 w	48 w	Then:	Unsch. (*6)
1.	Confirm eligibility	✓				✓						
2.	Consent confirmed	✓				✓*3						
3.	Medical history	✓										
4.	Baseline characteristics	✓										
5.	Vital signs	✓				✓	✓	✓	✓	✓	16 w+	✓
6.	Weight	✓				✓		✓		✓	16 w+	✓
7.	History directed medical exam	✓				✓	✓	✓	✓	✓	16 w+	✓
8.	Full blood count (FBC)	✓		✓		✓	✓	✓	✓	✓	16 w+	✓
9.	Liver function tests	✓		✓		✓	✓	✓	✓	✓	16 w+	✓
10.	Electrolytes profile	✓		✓		✓	✓	✓	✓	✓	16 w+	✓
11.	Glucose test	✓		✓								
12.	TB IGRA test	✓										
13.	Chest X-ray	✓										
14.	12-lead ECG*1	✓										
15.	MRI*1	✓										
16.	Syphilis test	✓										
17.	HIV test	✓										
18.	Hep B / Hep C test	✓										
19.	Lyme IgG/IgM Antibody Serology*1	✓										
20.	Varicella history	✓										
21.	Pregnancy test (women only)	✓										
22.	BCVA	✓		✓		✓	✓	✓	✓	✓	16 w+	✓
23.	OCT	✓				✓	✓	✓	✓	✓	16 w+	✓

No.	Data item to be collected	Screen/ baseline	Treatment run-in				RCT / OLE					
			1 st injection (wk 0)	4 w	8 w (phone call)	16 w / Rx	12 w	24 w	36 w	48 w	Then:	Unsch. (*6)
24.	Fundus colour imaging	✓				✓	✓	✓	✓	✓	16 w+	✓
25.	Autofluorescence (AF) imaging	✓				✓*2	✓*2	✓*2	✓*2	✓*2	16 w+*2	✓*2
26.	Fundus fluorescein angiogram (FFA)	✓				✓*2	✓*2	✓*2	✓*2	✓*2	16 w+*2	✓*2
27.	Clinical exam (including slit-lamp examination and indirect ophthalmoscopy)	✓		✓								
28.	Clinical exam for treatment failure (including slit-lamp examination and indirect ophthalmoscopy)					✓	✓	✓	✓	✓	16 w+	✓
29.	Telephone wellbeing review				✓							
30.	Adverse events		✓	✓	✓	✓	✓	✓	✓	✓	✓	✓
31.	EQ-5D-5L	✓			✓	✓	✓	✓	✓	✓	16 w+	✓
32.	VCM1	✓			✓	✓	✓	✓	✓	✓	16 w+	✓
33.	Symptoms of side-effects	✓			✓	✓	✓	✓	✓	✓	16 w+	✓
34.	WPAI-SHP questionnaire	✓			✓	✓	✓	✓	✓	✓	16 w+	✓
35.	Blood sample (for serum)*4	✓			✓	✓*4	✓*4	✓*4	✓	✓	48 w+*4	✓*4
36.	Blood sample (for DNA)	✓										
37.	Resource use				✓	✓	✓	✓	✓	✓	16 w+	✓

- Blood tests done as standard care can be accepted for screening up to a maximum of 3 months prior to the date of the screening visit. This can be extended in exceptional circumstances with approval of both the PI and CI.
- Chest x-ray, MRI and ECG done as standard care can be accepted for screening up to a maximum of 6 months prior to the date of the screening visit. This can be extended in exceptional circumstances with approval of both the PI and CI.
- Historic fundus colour, AF and FFA images can be accepted at baseline up to a maximum of 6 weeks prior to the date of the screening visit. This can be extended in exceptional circumstances with approval of both the PI and CI. OCT must be carried out at screening/baseline visit

- AF and FFA may not be necessary at baseline for those patients who do not need those assessments in order to support the clinical decision about TF. This is at the discretion of PI when determining activity or endpoint constitution of TF for individual patients.
- If AF/FFA are required to determine that disease is active or not at baseline, these tests will need to be repeated when establishing responder status or TF.
- Enrolment in the TRI (i.e. writing the TRI prescription) must be done up to 4 weeks after the date of the screening visit, but can be extended to 6 weeks in exceptional circumstances. If a patient is not enrolled within 6 weeks, the baseline ocular exams and imaging will need to be repeated to determine eligibility.
- TRI follow-ups start from the date of 1st injection (time 0); RCT follow-up starts from the date of randomisation. Repeat TRI follow ups start from date of treatment response assessment visit; repeat RCT follow up starts from date of treatment response assessment visit; OLE follow up starts from date of final RCT assessment visit.
- Visit windows: TRI +7 days; RCT -14 days and +7 days; OLE -14 days and +7 days.

\*1 Only required if clinically indicated.

\*2 Only required if undertaken at baseline to support the clinical decision about TF.

\*3 Written informed consent will be obtained at the start of the TRI; this consent will be confirmed among responders at the start of the RCT.

\*4 Only taken at these time points in the event of treatment failure being detected.

\*5 If patient has no history of varicella, advise to avoid people with chickenpox or shingles for duration of time on study medication.

\*6 If TF is suspected in between RCT follow up visits the participant should attend an unscheduled visit where the research team must complete all assessments as per scheduled RCT follow-up visits. If TF is confirmed not to have occurred participants must still attend the next scheduled visit and all assessments conducted as per protocol.

**BCVA** – best corrected visual acuity; **TF** – treatment failure; **OCT** – optical coherence tomogram; **Rx** – Randomisation; **VCM1** – Visual Function Questionnaire; **WPAI-SHP** – Work Productivity and Activity Impairment Questionnaire: Specific Health Problem Questionnaire; **w** - weekly; **w+** - weekly thereafter

## 6.6 Source data

Source data will differ for different items of data.

- Items 1-22, 27-30 and 37: paper CRFs designed specifically to capture the required data for the study (item 37 prescribed medication source data is the eCRF);
- Items 23-26: OCT, fundus, autofluorescence and fundus fluorescein angiography images submitted for independent grading;
- Items 31-34: Completed questionnaires returned by participants;
- Items 35-36: not applicable; samples for storage only (for future research).
- IMP accountability: IMP-Track Investigational Medicinal Product Management System

## 6.7 Planned recruitment rate

Projecting recruitment is complicated because: (a) estimates of several parameters are uncertain, (b) participants will be recruited with both incident (active) and prevalent (inactive) ANIU and (c) the TRI design causes a lag. Table 2 shows our projection with the assumptions described in a footnote.

## 6.8 Participant recruitment

Patients with ANIU present to, and are managed by, specialist ophthalmologists staffing clinics in tertiary hospitals which treat autoimmune ophthalmic diseases. Clinics will include new patients with ANIU and existing patients who are having ongoing treatment monitored. The eligibility criteria allow recruitment of either kind of patient. New patients started on treatment with oral prednisolone will be eligible, with an attempt being made to reduce oral prednisolone to  $\leq 5.0$  mg over 16 weeks alongside treatment with adalimumab. Existing patients who are already being treated but who require  $>5$ mg/day oral prednisolone will also be eligible, with an attempt being made to reduce oral prednisolone to  $\leq 5.0$  mg over 16 weeks alongside treatment with adalimumab. Both new patients and existing patients may be prescribed other non-biologic IMT in addition to oral prednisolone at the discretion of the clinician.

Potential participants will initially be screened from their medical records by the direct care team according to local hospital processes. Patients who are initially eligible will be given or sent an invitation letter and a patient information leaflet (PIL) describing the study. Potential participants will be given time to read the PIL and to ask questions that they may have; the person taking consent will discuss the trial with the potential participant prior to consent. Consent will be taken in clinic. The PIL will describe both the TRI period and the RCT, and the informed consent form (ICF) will include consent to both phases of the trial. Consented participants will undergo further screening assessment to determine their full eligibility to participate. Consented participants who meet all eligibility criteria will be enrolled in the TRI. Eligibility will be confirmed by a clinician on the delegation log. Participants who are classed as responders at the end of the TRI will be asked if they are willing to continue to the randomised phase of the study, before carrying out randomisation; their willingness to continue will be recorded at the time.

At their last visit before expiry of the placebo, participants who give consent will transition to the OLE.

**Table 2 projected recruitment of participants with active and inactive ANIU**

Trial month	Trial phase	Main trial activity	Number of centres	ANIU eligible for TRI		Number randomised	
				Inactive	Active	per month	cumulative
1 to 7	Pilot	Setup	0	0	0	0	0
8	Pilot	Recruit; TRI only	3	4	1	0	0
9	Pilot	Recruit; TRI only	5	6	2	0	0
10	Pilot	Recruit; TRI only	7	9	3	0	0
11	Pilot	Recruit; TRI only	9	11	4	0	0
12	Pilot	Recruit & rand'x	11	14	5	2	2
13	Pilot	Recruit & rand'x	13	16	6	4	6
14	Pilot	Recruit & rand'x	15	19	7	5	11
15	Pilot	Recruit & rand'x	17	21	8	7	18
16	Pilot	Recruit & rand'x	19	24	9	8	26
17	Pilot	Recruit & rand'x	19	24	9	10	36
18	Pilot	Recruit & rand'x	19	24	9	11	47
19	Pilot	Recruit & rand'x	19	24	9	13	60
20	Main RCT	Recruit & rand'x	19	20	9	14	74
21	Main RCT	Recruit & rand'x	19	18	9	14	88
22	Main RCT	Recruit & rand'x	19	15	9	14	102
23	Main RCT	Recruit & rand'x	19	13	9	14	116
24	Main RCT	Recruit & rand'x	19	10	9	13	129
25	Main RCT	Recruit & rand'x	19	8	9	12	141
26	Main RCT	Rand'x only	19	0	0	10	151
27	Main RCT	Rand'x only	19	0	0	9	160
28	Main RCT	Rand'x only	19	0	0	7	168
29	Main RCT	Rand'x only	19	0	0	7	174
30 to 41	Main RCT	Follow-up only	19	0	0	0	174
42	Main RCT	follow-up	19	0	0	0	174
43	Main RCT	d-b lock	19	0	0	0	174
44 to 46	Main RCT	analysis	19	0	0	0	0
47 to 48	Main RCT	write-up	19	0	0	0	0
Total				285	129	174	

Footnote: rand'x – randomise; annual incidence, 0.0003 [30]; prevalence, 0.00083 [30]; ANIU proportion >20yrs, 0.763; total incident cases, 12541; total prevalent cases, 34696; centres treating ANIU, 30; incident ANIU/centre/year, 418; prevalent ANIU/centre/year, 1157; p("eligible"), 0.06; p(approached), 1.00, p(ineligible after approach), 0.20; p(consenting for TRI), 0.40; p(responding), 0.50; p(available to randomise at end of TRI), 0.15; number of centres, 19.

## 6.9 Discontinuation/withdrawal of participants

As described in section 5.1, we will try to keep all participants in the RCT until the last participant has completed the 12-week visit in the RCT. Participants who consent to join the OLE may be followed for up to a further 76 weeks (approx. 18months). Each participant has the right to withdraw at any time. In addition, the investigator may withdraw the participant from treatment with adalimumab/placebo if continuation is considered not to be in the best interests of the participant, e.g. following a SAE or pregnancy. Participants must also stop treatment with

adalimumab/placebo after a maximum of two treatment switches (see section 5.1). In all instances of stopping treatment with adalimumab/placebo we will request that participants continue to attend the scheduled research visits so that the relevant data can be collected. All data and samples collected will be analysed and stored unless a participant expressly requests that his/her data or samples be destroyed.

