Keeping participants in the RCT and OLE until the study will be closed to reporting requires a strategy for managing repeated TFs. In the event of a TF in either eye during the RCT, a participant will stop taking the IMP and re-start open label treatment with adalimumab. In effect, this is the same as re-entering the protocol for the TRI (with other medications, including oral prednisolone being prescribed at the discretion of the treating ophthalmologist). If the participant again meets the criteria for being a “responder” at 16 weeks, he/she will re-start trial follow-up (RCT2) but switch to the alternative IMP to the one provided at randomisation. If the participant does not meet the criteria for “responder” at 16 weeks, he/she will be withdrawn from the trial, without unmasking allocation. Consistent with the PPI consultation, a maximum of two switches will be allowed, i.e. adalimumab-placebo-adalimumab or placebo-adalimumab-placebo. In the event of a TF in either eye during the OLE, a participant will exit the trial (adalimumab is available in usual care for patients with active disease).

[figure not shown]
Although the switch feature may appear complicated, it has important advantages. It was considered equitable and welcomed during the PPI consultation because it ensures that a participant (classified as a “responder” at the end of the TRI) who is allocated to placebo in the RCT and suffers TF has a chance to receive active drug. We anticipate that the opportunity to receive the opposite IMP in the event of TF will encourage a participant to accept: (a) initial randomisation, (b) that adalimumab is “truly not for them” in the event of multiple TFs and (c) not disclosing allocation until the trial reports, even after withdrawal. It has elements of a cross-over design (considered impracticable because of the long time-course of remission and TF, and controlling disease activity in the event of TF) so provides extra information in a (non-random) subset of participants about outcome with both adalimumab and placebo.

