### **5.5 Key design features to minimise bias**

The placebo-controlled trial design (including concealed randomisation) will protect against bias arising from the randomisation process. In the RCT, it will also protect against bias due to deviations from intended interventions and bias in measurement of outcomes, since participants, clinicians and other staff caring for participants, members of the research team (except the study statistician) and participants will be masked to participants' allocations [54]. The success of masking will be assessed (participants and their care team may become unmasked due to side effects). These protections will not apply during the OLE.

The allocation will be stratified by centre to minimise confounding due to centre-specific factors. Applying standard protocols, pre-defining procedures for participant follow-up/data collection and applying the procedures to all participants in the same way will help to minimise bias due to deviations from intended interventions and bias in measurement of outcomes in the event of instances of unmasking. Adherence to all aspects of the protocol will be monitored.

Bias due to missing outcome data, i.e. systematic differences in withdrawals between the groups, will be minimised by: i) the offer of a switch in allocation in the event of TF; ii) maintaining regular contact with participants throughout the duration of the trial to maximise the proportion of participants for whom all outcome data are available. The Data Monitoring and Safety Committee (DMSC) will monitor attrition by group.

We will minimise bias in selection of the reported result by pre-specifying outcomes (see 5.8) and by writing a detailed statistical analysis plan in advance of locking the database at the end of data collection (see 7.1).

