### **Randomised trial (RCT)**

RCT dosing will commence 1 week after randomisation, with fortnightly 40mg injections of drug or placebo until the end of the trial (follow-up for between 12 weeks and 170 weeks, about 3 and 40 months).

In the RCT, in the event of TF in either or both eyes, the participant will be offered the opportunity to repeat the TRI. If TF is observed at the final assessment in the RCT, the participant will exit the trial.

The visit window for RCT follow up visits is -14 days to +7 days.

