### **Repeat TRI**

TRI dosing will commence 1 week after the date of the response assessment visit, with fortnightly 40mg injections of open label adalimumab for 16-weeks (8 injections in total).

At the end of the 16-weeks the participant's response will be assessed again. If the participant shows a response to treatment as per section 6.3.1, they can re-enter the RCT. If they do not respond, then they will exit the trial.

The visit window for the TRI response assessment visit is +7 days only.

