#### **6.11 Likely rate of loss to follow-up**

Assuming that 27% in the placebo group are free from TF 12 months after randomisation (estimated from placebo groups of the two trials with 40% active and 60% inactive disease [1, 4]), we have set a target sample size of 174 randomised participants. A study of this size will have 90% to detect a HR 0.5 at the 5% two-sided significance level, allowing for 10% loss-to-follow-up in the first 12 months.

There are no special features to minimise bias due to missing outcome data. Established methods will be used to maximise the proportion of participants for whom all outcome data are available and the proportion of participants who receive the intervention to which they were allocated. However, ANIU is a debilitating condition for patients who are affected and, subject to other comorbidities they experience, we expect participants to attend their follow-up visits as scheduled; these are set at the same frequency as required for usual care so extra research-only visits should be unnecessary.

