### **7. Statistical analyses**

#### **7.1 Plan of analysis**

The primary analysis of effectiveness will be restricted to data collected in the RCT. The data will be analysed according to intention to treat (ITT) and follow CONSORT reporting guidelines. Analyses will be adjusted for centre. The primary outcome, time from randomisation to first TF in the RCT, will be compared using survival methods, allowing for censoring of any participant who is lost to follow-up. Secondary outcomes up to the time of TF will be compared using a mixed linear or logistic regression model as appropriate, adjusted for baseline measures when available. These outcomes will be modelled jointly with the time to first TF. Changes in treatment effect with time will be assessed by adding a treatment x time interaction to the model and comparing models using a likelihood ratio test. Model fit will be assessed and alternative models and/or transformations (e.g. to induce normality) will be explored where appropriate. Frequencies of AEs will be described. Treatment differences will be reported with 95% CIs.

A secondary analysis will be carried out at the end of the OLE, including data from both the RCT and OLE, updating the primary analysis estimates. If additional first TFs are observed in the OLE, these will increase the precision of updated estimates of treatment effectiveness.

A further secondary analysis will include follow-up time after the first TF. A participant who experiences a first TF will restart adalimumab (repeating the TRI) for 16 weeks. If after 16 weeks the participant satisfies the criteria for being a responder, he/she will re-enter the trial treated with the opposite treatment to the one originally allocated (placebo if originally on intervention, or vice versa). Restarting treatment will become the time origin for the second period of follow-up. (This process can be repeated another time, in the event of a second TF, generating up to three discrete “disconnected” periods of follow-up. Follow-up will cease after a third TF.

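### Section 6.9 keeps everyone who stops trial treatment in scheduled data collection, but 5.1, 5.7 and 7.1 end it for repeat run-in non-responders and third failures, which exposes the economic and safety comparisons

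*Protocol*

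**What the plan says.** Protocol 6.9 requires trial treatment to stop once two switches have been used. It then says: "In all instances of stopping treatment with adalimumab/placebo we will request that participants continue to attend the scheduled research visits". The purpose given is data collection, and no reason for stopping is excepted.

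Other sections say the opposite about some of the same people. In 5.1, a participant who has a TF, repeats the run-in and does not meet the responder criteria at 16 weeks is handled thus: "he/she will be withdrawn from the trial, without unmasking allocation". Section 5.7 (Repeat TRI) agrees: "If they do not respond, then they will exit the trial". Section 7.1, describing the analysis of several follow-up periods per participant, adds: "Follow-up will cease after a third TF".

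The statements on missing data also pull in different directions. Section 5.5 says that "systematic differences in withdrawals between the groups, will be minimised by" the offer of a switch after TF and regular contact with participants, with attrition by group monitored by the DMSC. Section 6.11 says: "There are no special features to minimise bias due to missing outcome data". Its next sentence relies on established methods to keep outcome data complete.

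**The concern.** A site that follows 5.7 stops collecting data on a randomised participant because of that participant's outcome. A site that follows 6.9 asks the same person to keep attending. Practice may therefore differ between sites.

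The participants who leave are those whose uveitis failed and could not be brought back under control in 16 weeks, so their quality of life and costs are unlikely to be typical of their arm. Cost-effectiveness is objective C. Section 7.5 plans mean QALYs and costs per trial arm from EQ-5D-5L at each visit, with no cut at first TF. Section 9.2 ends adverse-event collection with follow-up.

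Section 5.5 counts the switch offer as a safeguard against unequal withdrawal. Because the switch is open only to those who respond again, the same feature also generates outcome-driven exits.

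**Working it through.** **1. The rules side by side**

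| Situation | 6.9 | Other section |
|---|---|---|
| No response in repeat run-in | Asked to keep attending (all instances of stopping) | 5.1: withdrawn; 5.7: exits |
| Third TF, two switches used | Asked to keep attending (the case it names) | 7.1: follow-up ceases |
| TF at the final RCT visit | No RCT visit remains | 5.7: exits; no RCT data lost |

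The first two rows conflict. The third does not cost any RCT visits.

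**2. Which analyses use data after first TF**

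- Primary outcome (5.8.1, 7.1): time to first TF. It is recorded before any of these exits.
- Secondary outcomes (7.1): compared up to TF and modelled jointly with it, so not affected.
- QALYs and costs per arm (7.5): no cut at first TF, so exposed.
- Adverse events over follow-up (9.2): exposed.
- Multi-period analysis (7.1): exposed, but the protocol already calls it non-randomised and potentially biased.

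**3. The plan's own sample size**

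Inputs (5.9): 27% TF-free on placebo at 12 months, HR 0.5, 90% power, 5% two-sided, 10% loss.

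- TF-free on adalimumab: 0.27^0.5 = 0.520.
- Events (Freedman): (1.960 + 1.282)² × (1.5/0.5)² = 10.51 × 9, about 95.
- Mean event probability: 1 − (0.270 + 0.520)/2 = 0.605.
- N = 95/0.605 = 157; 157/0.90 = 175, against 174 stated.

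The figure reproduces. It concerns first TF only, so exits after first TF change neither N nor power.

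**4. How many might exit by week 52**

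Assumptions: exponential times; TF detected at once; 16-week repeat run-in; participant has 52 weeks of potential RCT follow-up. Hazards per week: placebo −ln(0.27)/52 = 0.0252; adalimumab half of that, 0.0126. First TF by week 52 is then 73% and 48%.

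The only response rate in the documents is 0.50, for the first run-in (Table 2 footnote). The rate *r* in a repeat run-in is not given and is varied here.

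First repeat run-in alone: to exit by week 52 a participant must fail by week 36, so the share is (1 − r) × (1 − S(36)).

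- Placebo, r = 0.5: 0.5 × (1 − 0.27^(36/52)) = 0.5 × 0.596 = 30%.
- Adalimumab, r = 0.5: 0.5 × (1 − 0.52^(36/52)) = 0.5 × 0.364 = 18%.

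A simulation that adds later periods and third failures gives:

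| Assumed repeat response | Placebo arm | Adalimumab arm |
|---|---|---|
| 0.5 after either | 31% (27 of 87) | 20% (17 of 87) |
| 0.7 after either | 19% | 12% |
| 0.8 after either | 13% | 8% |
| 0.7 after placebo, 0.3 after adalimumab | 21% | 26% |

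Third failures are under 1% by week 52 in every row. Nearly all exits are repeat run-in non-responders.

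**The case against.** The strongest reply is that ending follow-up after repeat non-response is a deliberate design feature, stated in both 5.1 and 5.7, and that little depends on it. Much of this stands. A reader might infer that the primary result or the comparisons of visual acuity and visual function are biased. The documents do not support that, because the primary outcome is first TF and 7.1 compares secondary outcomes only up to TF.

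A reader might also set the exit shares against the 10% loss allowance and conclude that the trial is underpowered. That allowance belongs to the sample size for first TF, and exits after first TF do not draw on it.

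The size and direction are uncertain. Everyone in a repeat run-in has responded once before, so 0.50 may be too low. If response is poorer after failing on adalimumab, that arm loses more. Projections beyond a year would mislead, because RCT follow-up runs from 12 to 170 weeks and many participants will not reach two years.

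The sentence in 7.1 about a third TF can be read as describing analysed periods, not as an instruction to sites, and the numbers are small. Section 6.11 does not deny all protection; it relies on established methods. Section 6.9 only requests attendance.

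Timing also matters. The current version is dated 22 September 2025. Final RCT visits fall before 31 January 2025 (5.1, 5.7) or 31 January 2026 (1.1), so new wording would recover few visits or none.

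What remains is a direct conflict between 6.9 and both 5.1 and 5.7 about the same participants, with consequences for a stated objective.

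**Conclusion.** The contradiction holds, and the passages must be reconciled. Its reach is limited to data after first TF: the per-arm QALY and cost comparison, adverse events over follow-up, and the multi-period analysis. Under 5.1 and 5.7 these lose participants because of outcome.

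In the scenarios run, between 8% and 31% of an arm would exit within 52 weeks, for participants with that much potential follow-up. Visit-based detection of TF would delay exits, and shorter follow-up would lower the share of the whole arm. Loss is probably unequal, since the planning rates put first TF at 73% against 48%, and 7.1 itself expects later periods to be unbalanced. Which arm loses more cannot be settled from the protocol, because the repeat response rate is an assumption.

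This should be corrected, but it does not threaten the primary conclusion.

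**What to change.** 1. Let the 6.9 data-collection rule govern. In 5.1, 5.7 and 7.1, state that a repeat run-in non-responder, or a participant with a third TF, stops trial treatment but is asked to continue scheduled data collection until the RCT ends, with at least EQ-5D-5L, resource use and adverse events.
2. Align the note under Table 1, which counts repeat run-in and repeat RCT visits from the response assessment and gives no visit origin for someone who has stopped. Align the adverse-event period in 9.2, which ends at the run-in for non-responders who leave.
3. Record *stopped trial treatment* and *withdrew from follow-up* as separate events.
4. Reconcile the 6.11 sentence with the measures listed in 5.5.
5. For participants who have already exited, report numbers and reasons by arm and say which rule was applied. Handle missing post-exit EQ-5D and cost data explicitly in the economic analysis, with a sensitivity analysis that does not assume missing at random. Given the dates, this may be the part with most effect.

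The cost is a wording amendment, a status field on the CRF, and some extra questionnaires and data entry; 6.11 says visits match usual-care frequency. Some participants will decline. No treatment rule changes.
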